10.4. FOLLOW-UP EVALUATIONS

The follow-up evaluations will occur at 3 Months, 6 Months and 12 Months after the index procedure and include an assessment of device-related adverse events/incidents, evaluation using the SF-36 PCS and MCS scores, as well as clinical assessment of bone consolidation. Investigators should consider weight-bearing, pain and imaging when assessing bone consolidation. See the section below for visit windows and a list of assessments to be performed at each visit.

100 St. 100 St.

Investigative site personnel will contact subjects prior to their scheduled follow-up evaluations to encourage compliance with clinical investigation visits and participation.

If a subject misses a visit and is outside of the visit window, every effort should be made to collect data instead of noting the visit as missed.

10.5. SCHEDULE OF EVENTS

Assessment	Initial Assessment	3 Months a, b (+/-2 weeks)	6 Months a, b (+/-3 weeks)	12 Months ^b (+/-4 weeks)
Informed Consent	X ^c			
Demographics & Medical History	X			
Inclusion/Exclusion	X			
Primary Diagnosis	X			
Surgical Procedure	X			
Clinical Assessment of Bone Consolidation d, e		X	X	X
SF-36v2 (PCS & MCS)	X ^f	X	X g	X g
Subject Disposition h		X	X	X

Device-Related Adverse Events/Incidents & Reoperations will be collected throughout the course of the Clinical Investigation.

- a. Follow-up visit schedule to reflect Institutions' Standard of Care practices
- b. If the subject missed a visit and outside of visit window, every effort should be made to collect data instead of noting visit as missed. Visit windows are calculated from the index event, and not from the previous visit.
- c. Informed consent must be obtained prior to enrollment in the study (i.e., prior to performance of any study-related activities).
- d. Once bone consolidation is observed, assessment no longer needs to be conducted at the additional follow-up visits.
- e. Investigators should consider weight-bearing, pain and imaging when assessing bone consolidation.
- f. SF-36v2 evaluation must be collected post-informed consent.
- g. If bone consolidation is previously observed at the previous follow-up visit, evaluation is to be collected via phone.
- h. Subject Disposition assessment would occur at any time point for subject withdrawal prior to the completion of the clinical investigation.

0.00

11. Statistical Methods

The Statistical Analysis Plan (SAP) lists all variables/questions within this clinical investigation. Therefore, no additional "evaluation" chapter is required and needed for this CIP.

Data will be captured via IBM Merge EDC system and statistical analysis will be performed using IBM SPSS. All statistical hypotheses tests will be with confidence levels (1- α) of 95% and power (1- β) of 80%. The significance level (α) is 0.05 and the beta-value (β) is set to 0.20. Therefore, p-values \leq 0.05 will indicate statistical significance.

Results will be presented using summary tables and optionally supported by graphs. For detailed information per variable, see SAP.

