Chan et al.	SP	46.00	47.00	included
Sanders et al.	SP	40.80	46.00	included
Sun et.al.	SP	49.41	44.71	included
Sun et.al.	IP	43.21	43.81	included
Wang et.al.		79.10	77.00	excluded

Summary of explorative analysis is listed below:

18215 54 30

			Statistic	Std. Error
SF-36 PCS Physical at 12	Mean		43,4840	1,98495
months post-op	90% Confidence Interval	Lower Bound	39,2524	
	for Mean	Upper Bound	47,7156	
	Median		43,2100	
	Std. Deviation		4,43849	
	Minimum		38,00	
	Maximum		49,41	
	Range		11,41	
	Interquartile Range		8,31	
SF-36 PCS Mental at 12	Mean		45,7040	,63333
months post-op	90% Confidence Interval for Mean	Lower Bound	44,3538	
		Upper Bound	47,0542	
	Median		46,0000	
	Std. Deviation		1,41617	
	Minimum		43,81	
	Maximum		47,00	
	Range		3,19	
	Interquartile Range		2,74	

As the mean physical score (PCS) was slightly lower, it was used for the sample size calculation.

For the clinical investigation the one-sided 95% confidence interval will be applied.

Acceptance Criteria for Sample Size Calculation					
Significance Level (α)	0.05 (5%)				
Power (1-β)	0.80 (80%)				
Confidence Interval (CI)	0.95 (95%)				
Tails	1				
Path	Non-inferiority T2 Alpha Tibia (A) ≥ Benchmark (B, pooled benchmark results)				
Hamathagas Dain	Null (H ₀)	$A - B < -\theta$			
Hypotheses Pair	Alternative (H ₁)	$A - B \ge -\theta$			
Benchmark Timepoint	12 months post-operative				
Benchmark Mean	43.48 points SF-36 PCS at 12 months (IP an	d SP together)			
Benchmark Std. Dev.	No standard deviation results were given by Chan et al., Sanders et al. nor b Wang et al. Only Sun et al. reported standard deviations at 12 months postoperative for SF-36 PCS of 6.27 for the SP and of 6.52 for the IP subgroup As a worst-case, the double standard deviation reported by Sun et al. was used for the sample size calculation (2 * 6.52 = 13.04 points)				
Benchmark 90% CI of Mean	Lower 90% CI: 39.25 (two-sided 90% CI equals a one-sided 95% CI)				
Denchmark 90% CI of Mean	Upper 90% CI: 47.72				
Margin (-θ)	Lower 90% CI of Benchmark: 39.25				
Software Used	IBM SPSS Sample Power V3.0				

IBM SPSS Sample Power Output

One goal of the proposed clinical investigation is to test the null hypothesis that the population mean is 39.25. The criterion for significance (alpha) has been set at 0.050. The test is 1-tailed, which means that only an effect in the expected direction will be interpreted.

[figure not shown]

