With the proposed sample size of 61 subjects, the clinical investigation will have power of 80.0% to yield a statistically significant result.

This computation assumes that the population from which the sample will be drawn has a mean of 43.48 with a standard deviation of 13.04. The observed value will be tested against a theoretical value (constant) of 39.25.

This effect was selected as the smallest effect that would be important to detect, in the sense that any smaller effect would not be of clinical or substantive significance.

A second goal of this clinical investigation is to estimate the mean in the population. On average, a clinical investigation of this design would enable us to report the mean with a precision (95.0% confidence level) of plus/minus 2.77 points.

The precision estimated here is the median precision. Precision will vary as a function of the observed standard deviation (as well as sample size), and in any single clinical investigation will be narrower or wider than this estimate.

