To test non-inferiority, the 12 months mean SF-36 PCS result of the T2 Alpha Tibia group will be compared to the mean estimate of the control group, 43.48 points.

To be able to identify an acceptable difference or zone of indifference $(-\theta)$, the lower 90% confidence interval (CI) of the SF-36 PCS result at 12 months post-operative in the control group (Sanders, et al.; Sun, et al.; Chan, et al.) was used as lower limit (lower 90% CI of control is 39.25 points). The maximum acceptable difference in the negative direction is 4.23 points.

Based on the underlying distribution of the data and the result of the normality assessment, either the parametric one-sample t-test or the non-parametric one-sample sign test will be used to compare the 12 months post-operative SF-36 PCS result of the T2 Alpha Tibia group against the value of 39.25 points (mean of control - θ or 43.48 – 4.23 = 39.25 points).

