Sun et.al.	SP	49.41	44.71	included
Sun et.al.	IP	43.21	43.81	included
Wang et.al.		79.10	77.00	excluded

Summary of explorative analysis is listed below:

Descriptives

			Statistic	Std. Error
SF-36 PCS Physical at 12	Mean		43,4840	1,98495
months post-op	90% Confidence Interval	Lower Bound	39,2524	
	for Mean	Upper Bound	47,7156	
	Median		43,2100	
	Std. Deviation		4,43849	
	Minimum		38,00	
	Maximum		49,41	
	Range		11,41	
	Interquartile Range		8,31	
SF-36 PCS Mental at 12	Mean		45,7040	,63333
months post-op	90% Confidence Interval	Lower Bound	44,3538	
	for Mean	Upper Bound	47,0542	
	Median		46,0000	
	Std. Deviation		1,41617	
	Minimum		43,81	
	Maximum		47,00	
	Range		3,19	
	Interquartile Range		2,74	

As the mean physical score (PCS) was slightly lower, it was used for the sample size calculation.

For the clinical investigation the one-sided 95% confidence interval will be applied.

Acceptance Criteria for S	Sample Size Calculation			
Significance Level (a)	0.05 (5%)			
Power (1-β)	0.80 (80%)			
Confidence Interval (CI)	0.95 (95%)			
Tails	1			
Path	Non-inferiority T2 Alpha Tibia (A) ≥ Benchmark (B, pooled	benchmark results)		
Hamadhasan Dain	Null (H ₀)	$A - B < -\theta$		
Hypotneses Pair	Alternative (H ₁)	$A - B \ge -\theta$		
Benchmark Timepoint	12 months post-operative			
Benchmark Mean	43.48 points SF-36 PCS at 12 months (IP an	d SP together)		
	No standard deviation results were given by Wang et al.	Chan et al., Sanders et al. nor by		
Benchmark Std. Dev.	• Only Sun et al. reported standard deviations at 12 months postoperative for SF-36 PCS of 6.27 for the SP and of 6.52 for the IP subgroup			
	As a worst-case, the double standard deviation for the sample size calculation $(2 * 6.52 = 13)$	on reported by Sun et al. was used 3.04 points)		
Benchmark 90% CI of Mean	Lower 90% CI: 39.25 (two-sided 90% CI e	quals a one-sided 95% CI)		

	Upper 90% CI: 47.72
Margin (-0)	Lower 90% CI of Benchmark: 39.25
Software Used	IBM SPSS Sample Power V3.0

IBM SPSS Sample Power Output

One goal of the proposed clinical investigation is to test the null hypothesis that the population mean is 39.25. The criterion for significance (alpha) has been set at 0.050. The test is 1-tailed, which means that only an effect in the expected direction will be interpreted.

With the proposed sample size of 61 subjects, the clinical investigation will have power of 80.0% to yield a statistically significant result.

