4.7. CONFIDENCE INTERVALS AND P-VALUES

The following acceptance / rejection criteria were used for this clinical investigation:

Parameter	Acceptance / rejection criteria
Confidence level (1-a)	0.95 (95%)
Significance level (α)	0.05 (5%)
Power $(1-\beta)$	0.80 (80%)
Beta-level (β)	0.20 (20%)
Confidence interval of mean	95%
p-value indicating significance	\leq 0.05

Table 4.7: Acceptance / Rejection Criteria

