6.7. ADDITIONAL ANALYSIS

6.7.1.SF-36 Total Physical Score Comparison

Evaluation	Level of	Analysis Blan			
Variable / Question	Measurement	Analysis Flan			
All Assessments – SF-36 Tota	al Physical Score	e Comparison			
Use "SF-36 Total Physical Score Pre-On Ipoints]" and "SF-36 Total Physical Score 3 Months Ipoints]":					
Based on the underlying distribution of the data in both groups and the result of the normality assessment, either					
the parametric paired samples t-test or the non-parametric Wilcoxon test will be used to compare "SF-36 Total					
Physical Score Pre-Op [points]" and	"SF-36 Total Physic	cal Score 3 Months [points]" to evaluate the SF-36			
PCS score change by subject (improvement or decrease).					
The complete available SPSS tables c	ontent related to eith	er the paired samples t-test or the Wilcoxon test will			
be included in the final report.					
(Variable(s): VISITDT; PCSSCORE)					
Use "SF-36 Total Physical Score Pro	e-Op [points]" and ".	SF-36 Total Physical Score 6 Months [points]":			
Based on the underlying distribution of	of the data in both gro	oups and the result of the normality assessment, either			
the parametric paired samples t-test of	r the non-parametric	Wilcoxon test will be used to compare "SF-36 Total			
Physical Score Pre-Op [points]" and	"SF-36 Total Physic	cal Score 6 Months [points]" to evaluate the SF-36			
PCS score change by subject (improv	ement or decrease).				
The complete available SPSS tables c	ontent related to eith	er the paired samples t-test or the Wilcoxon test will			
be included in the final report.					
(Variable(s): VISITDT; PCSSCORE))				
Use "SF-36 Total Physical Score Pro	e-Op [points]" and "	SF-36 Total Physical Score 12 Months [points]":			
Based on the underlying distribution of	of the data in both gro	bups and the result of the normality assessment, either			
the parametric paired samples t-test of	r the non-parametric	Wilcoxon test will be used to compare "SF-36 Total			
Physical Score Pre-Op [points]" and	"SF-36 Total Physic	cal Score 12 Months [points]" to evaluate the SF-36			
PCS score change by subject (improv	ement or decrease).	an the named complex t test on the Wilcower test will			
he included in the final report	ontent related to entit	er me paried samples t-test of me wheoxon test will			
(Variable(s): VISITDT: PCSSCOPE)					
Use "SE 36 Total Physical Score 3	 Months Ingints]" and	"SE 36 Total Physical Score 6 Months Incints".			

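### Protocol section 11 states 80% power for all hypothesis tests, but only the primary t-test was powered; the sign-test alternative does not have 80% on the same planning inputs (58.4% at n = 61 if data are normal)

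*Protocol*

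**What the plan says.** Protocol section 11 (Statistical Methods) sets the general rule: "All statistical hypotheses tests will be with confidence levels" of 95% and power of 80%, with alpha 0.05 and beta 0.20. SAP 4.7 introduces its table with "The following acceptance / rejection criteria were used for this clinical investigation" and lists power 0.80 there, without naming a test.

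The calculation behind the 80% is in Protocol 11.1 and SAP 3.2. It concerns one test of the 12-month SF-36 PCS mean against the constant 39.25: "The criterion for significance (alpha) has been set at 0.050. The test is 1-tailed". The assumed population "has a mean of 43.48 with a standard deviation of 13.04". The result is: "With the proposed sample size of 61 subjects, the clinical investigation will have power of 80.0% to yield a statistically significant result". The software output shown in SAP 3.2 gives 0.805.

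The primary analysis is not fixed to that test. Protocol 11.3.2, SAP 3.1.1 and SAP 6.6 say that, depending on the normality assessment, "either the parametric one-sample t-test or the non-parametric one-sample sign test will be used". SAP 4.10 sends the analysis to non-parametric methods when normality fails, without transforming the data. Protocol 11.1 and SAP 3.2 themselves remark that summary scores usually depart from normality.

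SAP 6.7.1 adds six visit-to-visit comparisons of PCS, for which "the parametric paired samples t-test or the non-parametric Wilcoxon test will be used to compare" the two time points. No expected change, SD of change or sidedness is given for them.

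**The concern.** A power statement that covers every test needs a calculation for every test, or at least for each test that can decide the primary endpoint. Here there is one calculation, for the t-test. The sign test may carry the primary conclusion, and the plan's own remark about non-normal summary scores makes that route foreseeable, yet no power is given for it.

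What is at stake is the reading of a non-significant result. If the sign test failed to show non-inferiority, a reader relying on Protocol section 11 would take it as a negative result from a test with 80% power. The plan has not shown that. The same would apply to a null paired comparison.

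**Working it through.** **Inputs** (Protocol 11.1 and 11.3.2; SAP 3.2): n = 61; true mean 43.48; limit 39.25; difference 43.48 − 39.25 = 4.23; SD 13.04, which is twice 6.52, the larger of the two SDs given by the only literature source that reported any; one-sided alpha 0.05.

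**1. The plan's own figure.** Standardised difference: 4.23 / 13.04 = 0.324. Noncentrality: 0.324 × √61 = 2.53. Power is the probability that a noncentral t with 60 df exceeds the one-sided 5% critical value, which gives 80.5%. This agrees with the stated 80.0% and the software's 0.805. The normal approximation gives 81.3%.

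**2. Sign test, same inputs, normal data.** The test counts the values above 39.25.

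- Probability that one value exceeds 39.25: Φ(0.324) = 0.627.
- Critical count: the smallest r with P(Bin(n, 0.5) ≥ r) ≤ 0.05.
- Power: P(Bin(n, 0.627) ≥ r).

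| Evaluable n | Reject at | Actual size | Sign-test power | t-test power |
|---|---|---|---|---|
| 61 | 38 or more | 3.6% | 58.4% | 80.5% |
| 64 (80 less 20%) | 40 or more | 3.0% | 57.0% | 82.2% |
| 80 (no drop-out) | 48 or more | 4.65% | 73.4% | 89.1% |

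The small fall from 61 to 64 comes from the discrete critical count. Part of the shortfall at 61 is this discreteness too, but not all of it: rejecting at 37, which an uncorrected normal approximation would do at an actual size of 6.2%, still gives only 68.2%. On these inputs the exact test first reaches 80% at 100 evaluable subjects and stays there from 104.

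**3. How far the 58.4% depends on shape and SD.** The sign test is meant for data that fail the normality check, so the normal case is only a reference. With n = 61, rejection at 38 and mean 43.48:

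| Distribution | SD | P(X > 39.25) | Sign-test power |
|---|---|---|---|
| Normal | 13.04 | 0.627 | 58.4% |
| Logistic | 13.04 | 0.643 | 68.1% |
| t, 5 df | 13.04 | 0.654 | 74.1% |
| Laplace | 13.04 | 0.684 | 87.7% |
| Skew-normal, shape −2 | 13.04 | 0.656 | 75.2% |
| Skew-normal, shape −4 | 13.04 | 0.673 | 83.3% |
| Skew-normal, shape 2 | 13.04 | 0.600 | 40.9% |
| Skew-normal, shape 4 | 13.04 | 0.569 | 23.6% |
| Normal | 6.52 | 0.742 | 98.6% |

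The shapes are illustrative assumptions; the documents give none. The spread arises because the sign test responds to the share of values above 39.25, which the mean and SD do not fix.

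**4. Paired comparisons.** Power cannot be computed, because the documents give no inputs. Assuming 61 pairs and a two-sided 5% paired t-test, 80% power needs a mean change of about 0.365 SD of the change. Whether the true changes are larger or smaller than that is unknown.

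**The case against.** The strongest reply is that the sentence in Protocol section 11 only sets conventions: it fixes alpha and beta and then the p-value threshold. Section 11.1 follows directly, lists 0.80 among the sample-size criteria and shows exactly which test was powered. A careful reader is not misled. This has force as a reading of intent, but the sentence says all tests, and a later section relies on a second primary test to which the calculation does not apply.

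Other parts of the reply stand and limit the point:

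- A reader might infer that the stated power, or the sample size built on it, is wrong. It is not; the t-test figure reproduces.
- A reader might take 58% as the power of the sign test. It assumes normal data, the case in which that test would ordinarily not be chosen, and a deliberately doubled SD. Under other assumptions the power can lie above 80%.
- A reader might infer that the six paired tests are underpowered. Their power is unknown. They are additional analyses, outside the primary and secondary endpoints, and need no formal power.
- A reader might say that SAP Table 4.7 repeats the claim for all tests. It lists 0.80 without limiting it, but does not say that each test attains it.

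It can also be said that the decision table in Protocol 11.3.2 words a non-significant result as insufficient evidence, without invoking power. That is only partly reassuring, since the same entry also labels the outcome as the device being below control.

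**Conclusion.** The 80% power statement in Protocol section 11 is wider than the plan supports. It holds for the primary one-sample t-test. It does not hold for the sign test on the plan's own mean, SD, limit and alpha: with normal data the shortfall at n = 61 is 80.5 − 58.4 = 22.1 percentage points against the t-test, and power is still 73.4% if all 80 subjects are evaluable. The size of the shortfall is not a fixed property of the design. Across the shapes tried, with the planning mean and SD, sign-test power at n = 61 runs from about 24% to 88%; with SD 6.52 and normal data it is 98.6%. What can be said without those assumptions is that the plan has not established 80% power for this route. For the paired comparisons no power can be claimed in either direction.

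This is a fault in the scope of a statement. It should be corrected because the sign test may decide the primary endpoint, but it leaves the t-test sample size as it is.

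**What to change.** Limit the sentence in Protocol section 11, and annotate the power row of SAP Table 4.7, along these lines: *The 80% power applies only to the primary one-sample t-test of 12-month PCS against 39.25 (80.5% with 61 evaluable subjects, true mean 43.48, SD 13.04, one-sided 5%). No power is claimed for any other test.*

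If the sign test remains as the primary alternative, add its power in Protocol 11.1 and SAP 3.2 with the assumptions stated and a range, not as a single 58% figure. For n = 61: 58.4% for normal data with SD 13.04; about 24% to 88% for the skewed and heavy-tailed shapes above at the same mean and SD; 98.6% for normal data with SD 6.52. If one primary test is named in advance instead, only that test's power needs stating. A note in SAP 6.7.1 that the paired comparisons are exploratory would settle their status.

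The cost is wording in two documents and a less favourable figure for one route. It adds no subjects, visits or procedures.

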11.1. DETERMINATION OF SAMPLE SIZE

The 12 months post-operative results for subjects implanted with the Tibial Nail of the T2 Alpha Tibia Nailing System will be compared to a historical group and results reported by Wang, et al. (2017); Sanders, et al. (2014); Sun, et al. (2016); and Chan, et al. (2016) will serve as the control group for the T2 Alpha Tibia Nail subjects.

Hypotheses were developed to allow for a comparison of 12 months post-operative SF-36 Physical Component Summary (PCS) results and 12 months effectiveness/performance between these two populations.

Benchmark and Objectives for Planned Research				
Endpoint Non-inferiority related to the SF-36 Physical Component Summary (PCS) for subject undergoing infrapatellar (IP) and/or suprapatellar (SP) tibia nailing at 12 months post operative compared to the pooled literature control.				
Estimated drop- out rate	20% Source: "Stannard et al: Functional Outcome Following Intramedullary Nailing of the Femur. A Prospective Randomized Comparison of Piriformis Fossa and Greater Trochanteric Entry Portals JBJS 2011" Stannard et al. reported a lost to follow up rate of 19.6% (11/56). Note: The source of Stannard et al. was used for T2 Alpha Tibia as well as it represents a worst-case drop-out rate.			

Results as reported by Benchmark

Non-inferiority related to the SF-36 Physical Component Summary (PCS) for subjects undergoing infrapatellar (IP) or suprapatellar (SP) tibia nailing at 12 months post-operative.

The results from the sources Chan et al, Sanders et al., and Sun et al. were pooled to determine overall two-sided 90% confidence intervals of the mean SF-36 PCS (physical) and mean SF-36 MCS (mental) scores.

Note: The results reported by Wang et al. seemed to be based on a different calculation method for the determination of the SF-36 scores and it was not possible to evaluate, what exactly was done by the authors. The score values reported by Wang et al. are much higher compared to what was normally reported in the literature and what was defined in country specific weights and coefficients. Wang et al. reported median score values whereas the other authors reported means. As summary score results usually tend to deviate from normality, means and medians might differ significantly. Therefore, the results reported by Wang et al. were not included into the pooled analysis.

Source	Subgroup	Mean SF36- PCS	Mean SF36- MCS	Pooling
Chan et al.	IP	38.00	47.00	included
Chan et al.	SP	46.00	47.00	included
Sanders et al.	SP	40.80	46.00	included
Sun et.al.	SP	49.41	44.71	included
Sun et.al.	IP	43.21	43.81	included
Wang et.al.		79.10	77.00	excluded

Summary of explorative analysis is listed below:

18215 54 30

			Statistic	Std. Error
SF-36 PCS Physical at 12	Mean		43,4840	1,98495
months post-op	90% Confidence Interval	Lower Bound	39,2524	
	for Mean	Upper Bound	47,7156	
	Median		43,2100	
	Std. Deviation		4,43849	
	Minimum		38,00	
	Maximum		49,41	
	Range		11,41	
	Interquartile Range		8,31	
SF-36 PCS Mental at 12	Mean		45,7040	,63333
months post-op	90% Confidence Interval for Mean	Lower Bound	44,3538	
		Upper Bound	47,0542	
	Median		46,0000	
	Std. Deviation		1,41617	
	Minimum		43,81	
	Maximum		47,00	
	Range		3,19	
	Interquartile Range		2,74	

As the mean physical score (PCS) was slightly lower, it was used for the sample size calculation.

For the clinical investigation the one-sided 95% confidence interval will be applied.

Acceptance Criteria for Sample Size Calculation					
Significance Level (α)	0.05 (5%)				
Power (1-β)	0.80 (80%)				
Confidence Interval (CI)	0.95 (95%)				
Tails	1				
Path	Non-inferiority T2 Alpha Tibia (A) ≥ Benchmark (B, pooled benchmark results)				
Hamathagas Dain	Null (H ₀)	$A - B < -\theta$			
Hypotheses Pair	Alternative (H ₁)	$A - B \ge -\theta$			
Benchmark Timepoint	12 months post-operative				
Benchmark Mean	43.48 points SF-36 PCS at 12 months (IP an	d SP together)			
Benchmark Std. Dev.	No standard deviation results were given by Chan et al., Sanders et al. nor b Wang et al. Only Sun et al. reported standard deviations at 12 months postoperative for SF-36 PCS of 6.27 for the SP and of 6.52 for the IP subgroup As a worst-case, the double standard deviation reported by Sun et al. was used for the sample size calculation (2 * 6.52 = 13.04 points)				
Benchmark 90% CI of Mean	Lower 90% CI: 39.25 (two-sided 90% CI equals a one-sided 95% CI)				
Denchmark 90% CI of Mean	Upper 90% CI: 47.72				
Margin (-θ)	Lower 90% CI of Benchmark: 39.25				
Software Used	IBM SPSS Sample Power V3.0				

IBM SPSS Sample Power Output

One goal of the proposed clinical investigation is to test the null hypothesis that the population mean is 39.25. The criterion for significance (alpha) has been set at 0.050. The test is 1-tailed, which means that only an effect in the expected direction will be interpreted.

[figure not shown]
With the proposed sample size of 61 subjects, the clinical investigation will have power of 80.0% to yield a statistically significant result.

This computation assumes that the population from which the sample will be drawn has a mean of 43.48 with a standard deviation of 13.04. The observed value will be tested against a theoretical value (constant) of 39.25.

This effect was selected as the smallest effect that would be important to detect, in the sense that any smaller effect would not be of clinical or substantive significance.

A second goal of this clinical investigation is to estimate the mean in the population. On average, a clinical investigation of this design would enable us to report the mean with a precision (95.0% confidence level) of plus/minus 2.77 points.

The precision estimated here is the median precision. Precision will vary as a function of the observed standard deviation (as well as sample size), and in any single clinical investigation will be narrower or wider than this estimate.

